9.2 Determination of Sample Size

Approximately 300 subjects will be randomized and equally allocated to receive bexagliflozin tablets, 20 mg, or placebo.

The sample size calculation for this study is based on a two group t-test with a two-sided significance at the 5% level and the following assumptions:

- 1) The placebo-corrected population mean change from baseline to Week 24 in HbA1c in the dose group of 20 mg will be -0.4%.
- 2) The pooled standard deviation for the change from baseline to Week 24 in HbA1c for the active and placebo groups will be 1.0%.

Under the above assumptions, an estimated sample size of 133 evaluable subjects per treatment arm yields approximately 90% power to detect a treatment difference between bexagliflozin and placebo. A sample size of 150 per arm has been selected to account for a

potential 12% drop-out and to allow adequate safety evaluation. The total sample size for this study will be 300 subjects.

This study will be conducted at multiple investigative sites and will likely involve variable numbers of subjects at each site. Enrollment will be on a competitive basis but will be capped at 30 subjects from each site.

9.3 Analysis Populations

9.3.1 Intention-to-treat Analysis Set

All subjects who are randomized will be included in the Intention-to-treat (ITT) Analysis Set. All analyses of the ITT analysis set will be based on each subject's randomized assigned treatment. The ITT analysis set will serve as the primary set for the efficacy analyses.

9.3.2 Safety Analysis Set

All subjects who are randomized and take at least one dose of double-blind study medication will be included in the Safety Analysis Set. Safety analyses will be based on the medication that a subject was actually taken. The Safety Analysis Set is the primary analysis set for safety evaluation.

9.3.3 Per Protocol Analysis Set

The Per Protocol (PP) Analysis Set will include all subjects in the ITT analysis set who meet the study eligibility requirements and have no major protocol deviations that affect the validity of the efficacy measurements. Protocol deviations that may result in subject exclusion from the PP Analysis Set will be detailed in the Statistical Analysis Plan.

9.4 Demographics and Baseline Characteristics

Demographic and baseline characteristics will be summarized descriptively based on the ITT and PP (if applicable) analysis sets for each treatment group as well as for all subjects combined. Key variables include age, gender, race, ethnicity, baseline HbA1c values, blood pressure, body weight, body mass index (BMI in kg/m²), fasting plasma glucose level, eGFR, and anti-diabetic treatment status at screening (including type of therapy used [treatment naïve, metformin, sulfonylurea, DPP-4 inhibitor, alpha-glucosidase inhibitor, GLP-1 agonist, insulin]). In general, baseline measurement is defined as the last measurement prior to the first dose of double-blind medication.

9.5 Analysis of Efficacy

All efficacy analyses will be performed based on the ITT analysis set. The primary endpoint analysis will also be conducted using the PP Analysis Set (if deemed different from ITT analysis set).

For the primary endpoint of HbA1c change from baseline over 24 weeks of treatment, the MMRM analysis of covariance model (ANCOVA) with baseline HbA1c as a covariate will be fitted to the available data, incorporating all visits at which HbA1c was measured for each subject including the scheduled and the unscheduled visits for measurement of HbA1c (National Research Council, 2010). Treatment, visit, treatment-by-visit, and stratification factors for randomization (HbA1c level [7.0 to 8.5% or 8.6 to 10.5%], screening anti-diabetic treatment regimen [insulin treated, other], eGFR [30-44 or 45-59 mL/min/1.73m²]) will be applied as fixed effects. From this model, an estimate of the treatment difference at week 24 will be generated, as will an assessment of whether this estimate is significantly different when comparing at a two-sided 0.05 level of significance. An unstructured within-patient covariance structure will be assumed. If the model with the unstructured covariance structure does not converge, an autoregressive(1) covariance structure will be used. HbA1c values obtained after the start of rescue medication will not be excluded from this primary analysis.

The MMRM model is one approach to obtain treatment effect estimates in the presence of missing data. As sensitivity analyses for missing data, the following will be performed:

- 1) Missing HbA1c data will be imputed via multiple imputation (MI), following which the MMRM will be repeated on the complete datasets with results combined across complete datasets using standard MI techniques; HbA1c values collected after the start of rescue medication will not be considered missing.
- 2) Missing HbA1c data will be imputed via LOCF, following which the MMRM will be repeated; HbA1c values collected after the start of rescue medication will be considered missing.
- 3) HbA1c values collected after the start of rescue medication will be considered missing, and the MMRM analyses will be re-performed.

If it is deemed that the PP analysis set is different from the ITT analysis set, same analyses as described above will be conducted in PP analysis set as well.

9.5.1 Analysis of Dropouts Pattern

The early termination rate is estimated to be 12%. To the extent possible, attempts will be made to minimize the amount of missing data through measures planned in the study conduct.

The number, timing, pattern, reason for and possible implications of missing values in efficacy assessments will be investigated. The dropout patterns will be assessed by Kaplan-Meier plots if applicable to assess whether they differ between treatment groups.

9.6 Secondary Efficacy Analyses

To assess the treatment effect on the change of body weight in subjects with baseline BMI ≥ 25 kg/m² at week 24, an analysis of covariance model (ANCOVA) will be implemented using all available data at week 24 (values obtained after the start of rescue medication will not be excluded in the analysis). MMRM modeling approach will be utilized. The model will include treatment, visit, treatment-by-visit, randomization stratification factors, and the

baseline weight value as fixed effects/covariates. Least squares mean treatment differences between the bexagliflozin and placebo will be estimated from the model. The corresponding 95% CI and p-value will be provided.

The change in systolic blood pressure (SBP) in subjects with baseline SBP \geq 130 mmHg in the bexagliflozin group compared with placebo at week 24 will be analyzed using the similar method with baseline SBP measure as a covariate. The same analysis method applies for the testing of changes in HbA1c at week 24 for subjects with baseline eGFR 45-59 mL/min/1.73m², and for subjects with baseline eGFR 30-44 mL/min/1.73m².

All analyses will be conducted in ITT analysis set. A hierarchical testing procedure will be applied to above four endpoints in the sequence provided in [Section 9.1](#).

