The renal Na⁺/glucose transport protein SGLT2 actively transports extracellular glucose into cells using the driving energy of the transmembrane electrochemical potential for sodium ions. Individuals with disruptions in SLC5A2, the gene encoding SGLT2, exhibit prominent glucosuria in the absence of significant co-morbidities (Santer et al., 2003; van den Heuvel et al., 2002). The excretion of glucose in the urine of diabetic subjects in amounts comparable to or greater than that seen in individuals harboring loss of functions mutations in SLC5A2 has the potential to improve both fasting and postprandial hyperglycemia without increasing insulin secretion, causing weight gain, or inducing hypoglycemia. Several SGLT2 inhibitors have been approved as a single agent or in combination with other hypoglycemic agents for the treatment of patients with T2DM (Vivian, 2015; Whalen et al., 2015). Although the effectiveness of SGLT2 inhibitors, measured by glucosuria, is reduced as the glomerular filtration rate (GFR) decreases, the drugs have been well tolerated in general and substantial amount of urinary glucose is disposed in diabetic patients with chronic kidney disease. The effectiveness of SGLT2 inhibitors for HbA1c reduction in patients with moderate renal impairment has been demonstrated in clinical trials of canagliflozin (Gilbert, 2014; Kohan et al., 2014), dapagliflozin (Yale et al., 2013), and empagliflozin (FDA Medical review empagliflozin, reference ID: 3402257, page 102/319). Although the efficacy varied, all SGLT2 inhibitors produced HbA1c reductions in patients with GFR between 45 and 60. The clinical efficacy in patients with GFR between 30 and 45 varied among different SGLT2 inhibitors (Scheen, 2015).

In a trial assessing the cardiovascular hazards of administration of empagliflozin (EMPA-REG), diabetic patients with increased cardiovascular risk were treated with empagliflozin or placebo in combination with standard of care for approximately 3 years. The primary

composite outcome of death, MI, and stroke (MACE) occurred in 10.5% of patients in the empagliflozin groups and in 12.1% of the patients in the placebo group. The MACE hazard ratio for patients with eGFR < 60 was 0.78 favoring empagliflozin and there was no statistically significant difference between patients with normal and impaired renal function (Zinman et al., 2015).

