9 PLANNED STATISTICAL METHODS

9.1 General Considerations

The following sections provide a summary of the planned analysis of the trial but a complete statistical analysis plan will be developed as a separate document and will be the final plan. All statistical analyses will be performed using Version 9.2 or later of Statistical Analysis Software (SAS®).

In general, descriptive statistics (number of subjects [n], mean, standard deviation [SD], Q1, median, Q3, minimum, and maximum) will be presented for continuous variables, and frequency and percentage for categorical variables.

Unless otherwise specified, all tests will be two-sided using a 0.05 level of significance. All confidence intervals (CIs) will be two-sided 95% confidence intervals.

The primary superiority test on lowering of HbA1c at week 24 from baseline for bexagliflozin when compared to placebo will be conducted at 0.05 level of significance. If it is successful, the following hierarchical testing strategy will be followed in testing secondary efficacy end points in order to preserve experiment-wide type I error at 0.05:

1. Superiority test of the change in body weight in subjects with baseline body mass index (BMI) ≥ 25 kg/m² in the bexagliflozin group compared to the placebo group
2. Superiority test of the change in systolic blood pressure (SBP) over time in subjects with SBP ≥ 130 mmHg in the bexagliflozin group compared to the placebo group
3. Superiority test of the change in HbA1c over time in subjects with eGFR 45 to 59 mL/min/1.73m² in the bexagliflozin group compared to the placebo group
4. Superiority test of the change in HbA1c over time in subjects with eGFR 30 to 44 mL/min/1.73m² in the bexagliflozin group compared to the placebo group

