8.2.1. Key secondary efficacy endpoints and analyses

The primary superiority test on lowering of HbA1c at week 24 from baseline for bexagliflozin when compared to placebo will be conducted at 0.05 significance level. If it is significant, the hierarchical testing strategy will be followed to preserve experiment-wide type I error of 0.05. The key secondary efficacy end points will be tested in the order:

1. Superiority test of the change in body weight in subjects with baseline BMI ≥ 25 kg/m² at week 24 in the bexagliflozin group compared to the placebo group
2. Superiority test of the change in systolic blood pressure (SBP) over time in subjects with SBP ≥ 130 mmHg in the bexagliflozin group compared to the placebo group
3. Superiority test of the change in HbA1c at week 24 in subjects with eGFR 45 to 59 mL/min/1.73m² in the bexagliflozin group compared to the placebo group
4. Superiority test of the change in HbA1c at week 24 in subjects with eGFR 30 to 44 mL/min/1.73m² in the bexagliflozin group compared to the placebo group

These key secondary endpoints will only be tested sequentially when significant treatment differences are established for the primary efficacy endpoint in the comparisons between the bexagliflozin and placebo groups.

Analysis for key secondary endpoints will be based on the ITT Analysis Set and repeated for the PP Analysis Set.

8.2.1.1. Change in body weight from baseline to week 24 in subjects with a BMI ≥ 25 kg/m²

This will be tested if the change from baseline body weight is significantly different between bexagliflozin and placebo groups based on ITT analysis set for subject with a baseline BMI ≥ 25 kg/m². The comparison of change in body weight between randomized treatments at week 24 will be carried out using similar MMRM ANCOVA model stated in section 8.1.1. Treatment, visit, treatment-by-visit, region, baseline HbA1c level as continuous variable, screening anti-diabetic treatment regimen (insulin treated or other), baseline eGFR (<45 or ≥ 45 mL/min/1.73m²) will be applied as fixed effects. Corresponding baseline weight value will be used as additional covariate. Treatment comparison p-values and difference at week 24 will be estimated from the

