8.2.1.3. Change in HbA1c from baseline to week 24 by eGFR status

They will be tested following the hierarchical order specified in section 8.2. They will be analyzed using the same MMRM ANCOVA model stated in section 8.1.1.

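### The last gate in the hierarchy (HbA1c at eGFR 30-44 only after 45-59 is won) is valid, but costs power without lowering the maximum experiment-wide error

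*Protocol*

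**What the plan says.** Protocol 9.1 tests the primary HbA1c comparison at 0.05 and, if it succeeds, four secondary endpoints in fixed order: weight (BMI >=25), SBP (baseline SBP >=130), HbA1c at eGFR 45-59, HbA1c at eGFR 30-44. The last entry reads "Superiority test of the change in HbA1c over time in subjects with eGFR 30 to 44". Protocol 9.6 confirms the rule: "A hierarchical testing procedure will be applied to above four endpoints in the sequence provided in" Section 9.1.

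SAP 8.2.1 keeps the order, with last entry "Superiority test of the change in HbA1c at week 24 in subjects with eGFR 30 to 44", and SAP 8.2.1.3 says of the two eGFR tests: "They will be tested following the hierarchical order specified in section 8.2". A 30-44 claim therefore needs significant results for the primary, weight, SBP and 45-59. The only reason given for the sequence is control of the experiment-wide error at 0.05.

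Protocol 9.2 and SAP 3.7 plan for one overall HbA1c effect. Neither document gives an effect or power by eGFR group. SAP 13 forms the groups from baseline instead of screening eGFR.

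**The concern.** The two eGFR tests use different subjects, so a near miss at 45-59 says little about 30-44, yet it would block a formal claim there. The 30-44 group is the less certain one. The Protocol introduction reports that all agents in the class lowered HbA1c at GFR 45 to 60, and then says: "The clinical efficacy in patients with GFR between 30 and 45 varied among different SGLT2 inhibitors". If the gate protected the error rate, the lost power would be its price. If it protects nothing, the power is given away. What is at stake is a confirmatory statement about 30-44 when that group's own result is significant.

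**Working it through.** **Inputs**
- Level (Protocol 9.1): "Unless otherwise specified, all tests will be two-sided using a 0.05 level of significance".
- Effect, overall only (Protocol 9.2): "The placebo-corrected population mean change from baseline to Week 24 in HbA1c in the dose group of 20 mg will be -0.4" per cent.
- SD (Protocol 9.2): "The pooled standard deviation for the change from baseline to Week 24 in HbA1c for the active and placebo groups will be 1.0" per cent.
- 150 randomised per arm and 12% dropout (Protocol 9.2): 150 x 0.88 = 132 evaluable per arm.
- At least 135 subjects in each eGFR group (Protocol 3.2.3, SAP 3.5), so 135 to 165 of 300. Evaluable per arm per group: 135 x 0.88 / 2 = 59.4 to 165 x 0.88 / 2 = 72.6, or 66 for an even split.
- Assumptions not in the documents: the effect in each eGFR group; weight and SBP already passed and independent of HbA1c.

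**The plan's own figure.** Power = Phi(d x sqrt(n/2) / SD - 1.96). With d = 0.4 and n = 133: Phi(3.262 - 1.96) = 0.904 (0.901 with the t distribution). The stated 90% is reproduced.

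**Does the gate protect the error rate?** Remove it, but keep primary, weight and SBP in sequence ahead of both eGFR tests.
1. Both eGFR nulls true, and the groups make up the ITT set: the overall effect is zero, so the primary null is true. Any false claim needs a false primary rejection: at most 0.05.
2. Primary null true for any other reason: every false claim again needs that rejection first.
3. Primary null false, weight or SBP null true: a false rejection of that gate must come first: at most 0.05.
4. Primary, weight and SBP nulls all false: at most one eGFR null is true, so only one false claim is possible: at most 0.05.

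A simulation (4 million draws, two independent group statistics, primary as their information-weighted sum) agrees. With both nulls true, the error was 0.050 including the primary and 0.033 for the two eGFR claims alone. With one null true it was 0.024 to 0.050. The planned sequence has the same maximum, 0.050. With no primary gate at all it would be 1 - 0.95^2 = 0.0975.

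**What does the gate cost?** At -0.4 and 66 per arm, power in one group is Phi(0.4 x sqrt(33) - 1.96) = Phi(0.338) = 0.632, so 45-59 misses about 37% of the time. With equal groups, winning both implies a primary z of at least (1.96 + 1.96)/sqrt(2) = 2.77. The planned chance of a 30-44 claim is therefore the product, 0.632 x 0.632 = 0.400. Without the gate it is the chance that the primary and 30-44 are both significant, 0.621 by simulation. Loss = 1 - 0.400/0.621 = 36%.

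| Effect 45-59 / 30-44 | Planned | Without gate | Claims lost |
|---|---|---|---|
| -0.40 / -0.40 | 0.400 | 0.621 | 36% |
| -0.45 / -0.35 | 0.382 | 0.514 | 26% |
| -0.50 / -0.30 | 0.333 | 0.404 | 18% |
| -0.55 / -0.25 | 0.266 | 0.299 | 11% |
| -0.60 / -0.20 | 0.194 | 0.208 | 7% |

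At -0.4 in both groups, the loss is 31% if 45-59 has 165 subjects and 40% if it has 135. With an even split and SD 1.2 it is 49%.

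**Group definition.** Eligibility uses screening eGFR of 30 to below 60, but the tests use baseline eGFR, so some subjects may fall outside both groups. Step 1 is then not exact. With 5% to 20% of subjects outside and an effect of 0.4 or 0.8 in them alone, the simulated false-claim rate for the pair was 0.031 to 0.042. Groups of <45 and >=45 remove the gap.

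**The case against.** The strongest reply is that the sequence is valid and its order sensible: the better-supported group comes first, and the introduction expects glucosuria to weaken as GFR falls. That stands. There is no error, bias or inflated type I error here, only avoidable loss of power. It also limits the size. A reader might infer that about a third of valid 30-44 claims are lost. The documents do not support that as a general figure, because it needs the same -0.4 effect in both groups, while their rationale points to a larger effect at 45-59.

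Three further points stand as qualifications:
- Every probability is conditional on weight and SBP having passed. The documents give no power for those tests, so the unconditional gain is smaller by an unknown factor.
- A reader might infer from the synopsis, which states the 135-subject minimum only for 30-44, that the design favours that group. Protocol 3.2.3 and SAP 3.5 apply the minimum to each group.
- The analysis by eGFR group is planned in any case (SAP 8.1.3, with nominal p-values, and Figure 14.2.4). Only the confirmatory status is at stake.

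The objection does not show any benefit from the gate: removing it leaves the maximum error and the chance of a 45-59 claim as they are.

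**Conclusion.** The point holds as an efficiency improvement. Making 30-44 conditional on 45-59 does not lower the maximum experiment-wide error, because the primary test covers the joint null of the two groups. Given that weight and SBP have passed, with 66 evaluable per arm per group and SD 1.0, it costs 36% of 30-44 claims at -0.4 in both groups. It costs about 7% to 26% if the effect falls with eGFR around that average. Given the protocol's rationale, the lower range is the more likely. The loss would exceed 36% only under less favourable assumptions, such as a larger SD, a smaller 45-59 group or a weaker effect at 45-59.

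A reader might also infer that the eGFR tests could be released on the primary alone. They could not: run beside the weight test, with weight and one eGFR group null, the error can reach 0.0975.

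**What to change.** In Protocol 9.1 and 9.6 and SAP 8.2.1, keep primary, weight and SBP in sequence and replace steps 3 and 4 with: if the primary, weight and SBP tests are all significant, HbA1c in the two eGFR groups is tested in each group at two-sided 0.05, neither conditional on the other. Do not release these tests on the primary alone. Define the groups as baseline eGFR >=45 and <45, already the SAP's model factor (SAP 8.1.1), so that they cover the ITT set and the error control is exact. Align SAP 8.2.1.3 with this.

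The cost is a documented SAP and protocol amendment before unblinding, with IRB/IEC approval of the protocol change (Protocol 10.2), and a slight change of population for subjects whose baseline eGFR lies outside 30-59. SAP 13 refers to outliers already seen in the dataset, so the amendment should record that the change was made blind to treatment. No subjects or data are added, and no other test loses power.

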9.7 Other Efficacy Analyses

Changes in HbA1c, FPG, SBP/DBP, body weight, and albumin level in urine for all subjects during the treatment period will be summarized descriptively by each time point (i.e., Weeks 6, 12, 24). In addition, these endpoints may be analyzed using a similar MMRM model as used for the primary analysis of HbA1c to compare bexagliflozin with placebo.

Cumulative summary on the proportion of subjects achieving HbA1c < 7%, and the proportion of subjects achieving body weight reduction of at least 5% will also be presented.

Analyses will be conducted using ITT analysis set.

9.8 Analysis of Safety

All safety analyses will be conducted based on the Safety Analysis Set.

Safety data will include AEs, physical exam results, vital signs, ECG results, and clinical lab measurements of serum chemistry, hematology, serum lipids, glycemic control parameters and urine specimens. Observed data will be summarized using descriptive statistics by treatment group based on the Safety Analysis Set.

9.8.1 Adverse Events

Adverse events will be mapped to preferred term and body system using the Medical Dictionary for Regulatory Activities (MedDRA). AE records that begin at or after the first administration of investigational products are considered treatment emergent AEs (TEAEs). The number and percentage of subjects reporting TEAEs will be summarized for each treatment group by MedDRA system organ class and preferred term. Further summaries by severity, and by relationship to study treatment will also be provided. Drug-related AEs will be considered those to be at least possibly related to investigational product based on the investigator's assessment. The number and percentage of subjects reporting serious AEs, and the number and percentage of subjects reporting AEs leading to treatment discontinuation will also be summarized for each treatment group by MedDRA system organ class and preferred term.

